### The following documents are currently attached to this item:

There are no documents attached for this item.

### Subject compensation\*

Will subjects be financially compensated for their participation?

### The following documents are currently attached to this item:

There are no documents attached for this item.

## If there is subject compensation, provide the schedule for compensation per study visit or session and total amount for entire participation, either as text or separate document

25 dollars will be provided to each participant for her/his participation in year 1. An additional \$25 will be provided in year 2 and year 3 should they continue to participate in focus groups and evaluation sessions. Subjects participating in only the evaluation session with the walking task will be paid \$5.00 per walk taken with the robot. Subjects participating in only the corn toss session will be paid \$10.00. Subjects participating at The Forum at Rancho San Antonio will not be compensated financially, however, snacks and beverages will be provided. No compensation will be provided due to the fact that the focus groups will be considerably shorter and limited in scope.

### **Study Procedures**

### Suicidal Ideation and Behavior

Does this research qualify as a clinical investigation that will utilize a test article (ie-drug or biological) which may carry a potential for central nervous system (CNS) effect(s)?

No

### **Procedures**

Year 1: Need-finding focus groups of clinicians and elders will be conducted, consisting of no more than 8-10 persons at each session. The aim of the initial focus groups is to reconcile the needs of elders with the robot requirements in order to determine the robot behaviors. The focus groups will help define a set of robot behaviors critical to meeting the needs of elders. Some behaviors that may emerge are transporting objects, telecommunication, following, leading, monitoring, playing, coaching, escorting persons, etc. In a typical focus group session, participants will explain life at their location, create a prioritized list of key activities and needs in physical, cognitive and social domains, hear about the research and the current capabilities of the robot, describe how they could use the robot to meet needs and what may be lacking, and set-robot tasks list. The elders in the needs assessment focus group will

be those serving on the council of ELDERs for LIFE. A member check (respondent validation) will take place with certain members of the various focus groups. Development partners will be identified from the focus group sessions. They will meet quarterly with the team to address development issues with the robot .This team will function as the early assessors and will provide real time feedback. Additionally, residents at The Forum at Rancho San Antonio in Silicon Valley will provide feedback via need-finding focus groups during year 1. Year 2: The robot prototype, consisting of the mobile base and a limited gripper, will be tested at a LIFE-affiliated retirement community with the elders and caregivers. The robot tasks evaluated will be involve services aimed at providing reminders, transport, telepresence, games, etc. Later that year, another version of the robot prototype, consisting of the mobile base incorporating improvements from the 1st round of assessments and an arm plus an articulated gripper. will be tested with elders and clinicians for 3 weeks. The robot tasks evaluated will be those involving mobility and some manipulation services such as hydration, picking up and transport etc. Data will be analyzed and results on robots usability will be provided as feedback to the development team in order to improve the system. THE ABOVE SUMMARY PARAGRAPH WAS INCLUDED IN OUR INITIAL IRB SUBMISSION, APPROVED OVER ONE YEAR AGO. BELOW ARE SOME ADDITIONAL DETAILS WHICH ARE THE MAIN MODIFICATION TO THE PROTOCOL. 1.) Subjects will be consented and be provided with a demographic survey (see attached). 2.) The robot prototype will be pre-programmed to complete key activities while located on site (Mercy Douglas or LIFE). The key activities are: (1) Encouraging exercise and companionship via walking; and (2) Helping elders remain hydrated by transporting them water at a scheduled time. Clinicians and caregivers will be consulted to determine how to tailor robot tasks to each consented patient. 3.) During the walking companion task, the robot will ask ambulatory participants to walk with the robot for the recommended 15 minutes of exercise time, at least one time per day. The robot will arrive at the elder's apartment at a prescheduled time selected by him/her. The amount of time the elder spends walking with the robot may be adjusted should the clinician/caregiver recommend a shorter time period (e.g. the walk time may be decreased if a patient suffers from sciatica). 4.) During the hydration task, the robot will bring a an 8 oz. bottle of water and a bottle opener to the elder. The frequency in which the robot bring water to the elder will be based upon the recommendation of the clinician/caregiver. The base recommendation will be 6, 8 oz. glasses of water outside of meal times. An example of a modification to the base recommendation would be to increase the number of water bottles for those who have dry mouth, are on dialysis, or tend to forget to drink water (this is very common among the elderly population). For both the walking and hydration tasks, the patient can instruct the robot to return at a later time or to go away. All tasks will take place in the hallway either just outside of the participant's apartment or inside the apartment. There will be one observer on our team who will watch the robot-participant interaction and complete a checklist of usability and issues. There will be another observer on our team who will immediately ask the participant to complete a post robot assessment survey tailored to the task they just experienced. Example Procedure for the Walking Task Scenario: The robot approaches a participant and asks them if they want to go for their scheduled walk. The participant can say "yes" and go for the walk, "no", or reschedule the robot to come back at a later time. Observer #1 takes notes on the interaction and completes the relevant checklist items. If the participant goes for the walk, observer #2 asks them to complete the post-encounter survey. After each usability test period, participants and their caregivers will have the opportunity to fill out a global interaction survey about the experience and provide information on how to improve the robot for future usability testing periods. Procedure for corntoss game: 1.) Subjects will be consented and be provided with a demographic survey (see attached). 2.) The robot prototype will be pre-programmed to complete key activities while located on site (Mercy Douglas or LIFE). Participants will first play the corn toss game without the assistance of the robot. They will retrieve the 3 bags from an upper cabinet, and play game against another participant. The participants will throw 3 bags and scores will be assessed. The participants will retrieve their own bags. In the second session, participants will repeat these steps; however someone from the research team will retrieve bags for the participant. At this point, there will be a pause and participants will be asked survey questions. Next, the same steps will be repeated, however the robot will retrieve the bags with a gripper from the upper cabinet and hand to the participant. Finally, the game will be repeated, but the robot will retrieve the bags at the end. Evaluations will then be repeated at the end. Clinicians and caregivers will be consulted to determine how to tailor robot tasks to each consented patient. After each usability test period, participants and their caregivers will have the opportunity to fill out a global interaction survey about the experience and provide information on how to improve the robot for future usability testing periods. The entire interaction will last for 1.5-2 hours maximum. Year 3: An improved prototype, consisting of the mobile base incorporating improvements from the 1st round of assessments and an arm plus articulated gripper will be tested with elders and clinicians at LIFE and/or a LIFEaffiliated retirement community for 4 weeks. The robot tasks evaluated will involve mobility and complex manipulation services such as opening doors etc. Data will be analyzed and results on robots usability will be provided as feedback to the development team in order to improve system. Overall, focus groups will be used throughout to assess and evaluate users interaction and experiences. Data will be collected by the robot during user interactions and aspects of the data will be evaluated and discussed with focus group members to critically assess robot's utility and progress. Research questions R2 and R3 will be addressed. a. Key usability and acceptance of service features required for the development of new manipulation technology are affordable, safe, and usable will be identified and appropriate metrics developed. b. Health status of subject participant will be tracked over years 2 and 3 and correlated with robot service record with the participant. Training and evaluation: Before each version of the robot is placed into service, demonstration and training sessions will occur where all potential clinical and elder users will be invited to learn about the robot and the experiment. Those willing to participate in a week-long study will sign informed consents. Data will be collected from the robot during the testing service and post -interviews will be conducted with a subset of participants to assess acceptance, problems and productivity issues. Participating elder members must agree to wear a tracking bracelet that will serve as an identifier allowing the robot to recognize a person and as alternate means of gathering activity data.

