### **Characteristics of the Study Population**

### **Target population**

1. Three populations will be involved: 1. Elders who are members of Living Independently For Elders (LIFE) run by the University of Pennsylvania, School of Nursing and their caregivers will be recruited for the study. The elder members will be drawn from those participating in the LIFE-affiliated retirement community (Mercy Douglas or Kearsley) or those on the Council of Elders for LIFE or those at LIFE. Elders must be members of LIFE and live at a LIFE-affiliated retirement community or participate in the elder council. Members of LIFE are age 55 and older, in need of medical care or supportive services, are state-certified as nursing home eligible, live in certain areas in Philadelphia County, Pennsylvania, prefer to continue living in their community for as long as possible, can be safely served and able to pay privately or through Medicare. Members of LIFE at Kearsley and Mercy Douglas require more assistance with physical, cognitive and social functioning and are provided a 24hour interdisciplinary clinical staff to assist them in meeting needs. Members are 62 years and older, in imminent risk of a nursing home placement, attends LIFE center daily (day program), able to have activities of daily living (ADL) needs met by caregivers, able to pay required rent for apartment, and able to function safely in community with other elders. And for the purpose of earlier prototyping and obtaining faster feedback on designs, Savioke may conduct additional focus groups at The Forum at Rancho San Antonio a Continuing Care Retirement Community located in Silicon Valley. 2. Clinicians: Clinicians will be recruited from the clinical staff working at LIFE, Kearsley, and Mercy Douglas which consists of primary care physicians, nurses and nurse practitioners, certified nursing assistants, home health aides, licensed social workers, physical and occupational therapists, personal care workers, etc. Subjects will also be excluded if they do not understand the study and refuse to comply with procedures. Subjects will be excluded if they are unable to cognitively give consent. For the corn toss game, 30 participants will be recruited who are able to use both arms and reach up towards a cabinet, have a minimental score of 20 or higher, and are able to stand and reach

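### The hydration task's one example of changing the water amount gives dialysis as a reason for more, with no check for a fluid limit

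*Protocol*

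**What the plan says.** All of the hydration text is in the Procedures section of the Protocol, under Year 2. The purpose of the task is given as "Helping elders remain hydrated by transporting them water at a scheduled time". The starting amount is fixed: "The base recommendation will be 6, 8 oz. glasses of water outside of meal times". The rule for individual participants is "The frequency in which the robot bring water to the elder will be based upon the recommendation of the clinician/caregiver", and more generally "Clinicians and caregivers will be consulted to determine how to tailor robot tasks to each consented patient".

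One example of changing the base amount follows. It is to "increase the number of water bottles for those who have dry mouth, are on dialysis", with forgetting to drink as a third reason. No example of a reduction, no maximum and no check for a prescribed fluid limit is given. The participant keeps control at the door, since "the patient can instruct the robot to return at a later time or to go away".

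Three other sections bear on the point:

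- **Target population** describes round-the-clock "interdisciplinary clinical staff to assist them in meeting needs" for members at Kearsley and Mercy Douglas. Its exclusions concern understanding, compliance and capacity to consent. None concerns dialysis or fluid restriction.
- **Subject recruitment** provides for a review of LIFE medical records, without naming a fluid-limit item.
- **Potential Study Risks** lists fatigue, falls, frustration, contact with the gripper, discomfort or embarrassment, and bumping into the robot. It lists nothing about fluid intake.

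**The concern.** The example treats dialysis like dry mouth or forgetfulness, as a plain reason to bring more water. Many people on dialysis are told to limit fluid. That is general clinical knowledge, taken here as an assumption: it does not hold for every such person, and the Protocol says nothing about it either way. For a participant who does have a limit, the example steers whoever sets the schedule towards more water when less may be needed.

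What is at stake is participant safety. The study enrols people who are certified as eligible for nursing home care, and by naming dialysis the Protocol itself contemplates such participants in the task. Nothing statistical turns on it.

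**Working it through.** The Protocol states no figure that needs reproducing. The check is a short calculation of the base amount and a comparison of the relevant texts.

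**Amount delivered.** Inputs from Procedures: 6 servings of 8 oz. Conversion: 1 US fl oz = 29.5735 mL.

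- Base: 6 × 8 = 48 fl oz; 48 × 29.5735 = 1,420 mL, about 1.42 L.
- One further bottle: 8 × 29.5735 = 237 mL, about 0.24 L.

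The period is not stated; per day is the natural reading. The Protocol does not say how many bottles an increase would add, so the total after an increase cannot be computed. These are volumes brought to the participant, not volumes drunk.

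**Direction of the example.** Three reasons are attached to one verb, and the verb is an increase. Dry mouth and forgetting to drink both fit it. Reading the verb as a slip for a decrease would make those two reasons wrong, so the misplaced element is the dialysis item itself.

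**Does anything else in the Protocol act as a fluid-limit check?**

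| Provision | Section | What it does | Checks for a fluid limit? |
|---|---|---|---|
| Frequency set by clinician or caregiver | Procedures | Allows more or less water | Not required |
| Tailoring of tasks per participant | Procedures | Requires consultation | Not named as a topic |
| Participant may defer or refuse | Procedures | Allows a delivery to be declined | No |
| Observers, one with a checklist of usability and issues | Procedures | Watch the interaction | No |
| Medical record review | Subject recruitment | Precedes enrolment | Not named as an item |
| Exclusions | Target population | Understanding, compliance, consent | No |
| 24-hour clinical staff at Kearsley and Mercy Douglas | Target population | General care | Not required |
| Working with LIFE staff on unforeseen challenges | Potential Study Risks | General response | No |

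Several of these could bring a limit to light. None requires that anyone look for one.

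**Comparison with the walking task.** In the same section, the walking example is protective: the walk may be shortened for a participant with sciatica. The matching hazards, fatigue and falls, then appear in Potential Study Risks. The hydration task has neither a protective example nor a listed risk.

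**The case against.** The strongest reply is that the dialysis wording is only an illustration under a rule that already individualises delivery. The recommendation of the clinician or caregiver governs, and less water, or none, is fully consistent with it. The robot brings a bottle and nobody is required to drink it. Team observers are present, and the arm prototype tested on services such as hydration is in use for 3 weeks. The premise about fluid limits comes from outside the Protocol, so there is no internal contradiction.

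Most of this stands, and it sets the weight of the point. It does not remove it. An illustration guides the people being consulted, and this one is the only place where the Protocol says anything about dialysis and water.

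Two stronger readings are tempting and are not supported:

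- A reader might infer that the Protocol orders extra water for everyone on dialysis. It does not: the sentence is introduced as an example, sets no amount and binds nobody.
- A reader might infer from the staff list in Target population ("primary care physicians, nurses and nurse practitioners, certified nursing assistants, home health aides, licensed social workers, physical and occupational therapists, personal care workers") that people without medical or nursing training would mostly set the water schedule. That list describes where clinician participants are recruited and is left open-ended. It does not say who makes the recommendation. All that can be said is that the wording admits a caregiver's recommendation and does not require a physician or nurse to confirm a limit.

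**Conclusion.** The point holds as a conditional safety matter that should be corrected. The Protocol's one example of changing the water amount names dialysis, unqualified, as a reason for more. No fluid-limit check is specified, and no fluid-related risk is listed.

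Harm would require a participant on dialysis who has a fluid limit, a recommender who follows the example, and a participant who drinks the extra water. The conclusion rests on the stated clinical assumption. How many participants are on dialysis is unknown, and zero is possible. The base of about 1.42 L and the 0.24 L per added bottle describe delivery only; no size of harm can be derived from the document. Sample size, outcomes and analyses are untouched.

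**What to change.** **Procedures, hydration task.** Delete the dialysis item, so that the example of an increase covers only dry mouth and forgetting to drink. Add: *Participants on dialysis, or with any fluid restriction, receive water only within the limit confirmed from the record review or by their treating clinician before the hydration task starts.*

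**Potential Study Risks.** Add excess fluid intake during the hydration task to the list.

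The cost is a short wording amendment and one extra item in the record review and clinician consultation that are already planned. No visit, measurement or analysis changes.

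### Correlating health status with the robot service record cannot separate effect from tailoring or refusal for walking and water, so for these tasks it cannot answer R3

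*Protocol*

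**What the plan says.** All of the following is in the Protocol, Procedures, unless another section is named.

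- **The analysis.** Item b: "Health status of subject participant will be tracked over years 2 and 3 and correlated with robot service record with the participant". It follows directly on the statement that R2 and R3 will be addressed. R3 (Overall objectives) asks, among other things, which robot behaviors do most for elders' well-being.
- **Tailoring in general.** "Clinicians and caregivers will be consulted to determine how to tailor robot tasks to each consented patient".
- **Walking.** Only some elders are asked: "the robot will ask ambulatory participants to walk with the robot". The length can be cut: "The amount of time the elder spends walking with the robot may be adjusted should the clinician/caregiver recommend a shorter time period"; sciatica is the example given.
- **Water.** "The frequency in which the robot bring water to the elder will be based upon the recommendation of the clinician/caregiver". The example of a change from the base schedule is to "increase the number of water bottles for those who have dry mouth, are on dialysis, or tend to forget to drink water", and the last of these reasons is described as very common in the elderly.
- **Refusal.** "For both the walking and hydration tasks, the patient can instruct the robot to return at a later time or to go away".

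The Analysis Plan section covers coding of transcripts, demographic summaries and anticipated outcomes. It does not mention this correlation.

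**The concern.** The exposure in item b (how much service an elder had) is partly a consequence of the outcome (the elder's health). This is confounding by indication, with selective uptake on top.

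The examples push the two tasks in opposite directions. An elder with a painful condition may be set less walking. An elder with dry mouth, on dialysis or forgetful may be set more water. If neither service did anything, the set level of walking would tend to go with better health and the set level of water with worse health. R3 asks for a comparison between behaviors, and opposite biases distort exactly that comparison.

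Service received has a further problem: it also depends on whether the elder accepts, which may depend on health at the time.

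**Working it through.** **No figure to reproduce.** The protocol gives no sample size, test, significance level or expected correlation for item b. The defect follows from setting the passages side by side:

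| Route from health to service | Walking | Water |
|---|---|---|
| Who is offered the task | ambulatory elders only | no such limit stated |
| Clinician-set level | may be lowered, e.g. sciatica | may be raised, e.g. dialysis |
| Service received | elder may decline or defer | elder may decline or defer |
| Likely sign at set level, no effect | positive | negative |

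The numbers below are illustration only. Every input is assumed unless marked.

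**Inputs.** No service effect. Health before deployment h0 and later health h1 are standardized, with stability s = 0.7. A share f = 0.1 to 0.5 of elders is moved off the base schedule (15 minutes of walking and 6 bottles of water, both from Procedures). The latent correlation between tailoring and h0 is ρ = 0.3 to 0.5 in size. n = 30 or 60; the protocol does not state how many elders do these tasks, and the 155 enrolled include clinicians.

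**Step 1: set level, unadjusted.** With two levels, the actual minutes or bottles drop out and the expected correlation is

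|r| = s × ρ × φ(z_f) / √(f(1−f)), where φ(z_f) is the normal density at the upper f point.

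- f = 0.1, ρ = 0.3: 0.7 × 0.3 × 0.1755/0.300 = 0.12
- f = 0.5, ρ = 0.5: 0.7 × 0.5 × 0.3989/0.500 = 0.28

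So r is about −0.12 to −0.28 for water and +0.12 to +0.28 for walking. In simulation, p<0.05 occurs in about 9–32% of replicates at n = 30 and 14–59% at n = 60.

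**Step 2: set level, adjusted for h0.** If h0 is measured without error and is the only link between tailoring and later health, r falls to about 0 and p<0.05 to about 5%. With baseline reliability 0.6, it is 6–11% (n = 30) and 7–19% (n = 60).

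**Step 3: the tailoring reason also predicts later health.** Let the part of tailoring not explained by h0 have coefficient k = −0.2 on h1. The partial correlation given h0 is

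r = k√(1−ρ²) φ(z_f) / [√(f(1−f) − ρ²φ(z_f)²) × √(1−s²)], with √(1−0.49) = 0.714.

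- f = 0.1, ρ = 0.5: −0.2 × 0.866 × 0.1755 / (0.287 × 0.714) = −0.15
- f = 0.5, ρ = 0.3: −0.2 × 0.954 × 0.3989 / (0.486 × 0.714) = −0.22

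Adjusted, p<0.05 still occurs in about 11–21% (n = 30) and 20–39% (n = 60). In the same setting the unadjusted correlation is −(sρ + 0.2√(1−ρ²)) φ(z_f)/√(f(1−f)). For f = 0.5, ρ = 0.5 that is −(0.35 + 0.173) × 0.798 = −0.42, against −0.21 after adjustment. Adjustment reduces the bias and does not remove it.

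**Step 4: service received.** Received = level × acceptance, with acceptance mean 0.70 and SD 0.15, and altered levels of 8 bottles and 10 minutes.

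- Acceptance unrelated to health: water r is −0.05 to −0.16, walking +0.05 to +0.19.
- Acceptance correlated 0.3 with current health: water turns positive, +0.09 to +0.22, and walking is +0.31 to +0.39. After adjustment for h0, water is still about +0.17 to +0.20 and walking +0.15 to +0.20.

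For water received, even the sign of the bias depends on who refuses.

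**The case against.** **The crude analysis is a reading, not a commitment.** Item b says only that the two will be correlated. It does not say between-person or unadjusted, and tracking over two years would allow a within-person analysis. Model and covariates are commonly left to a SAP, which is not shown. This stands in part: a reader might infer that the protocol commits to a crude correlation, and it does not. But no other analysis is stated, and no later plan can adjust for a set level or tailoring reason that was never recorded. Changing health could also drive both tailoring and refusal within one person.

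**Item b does not itself claim an effect.** This is correct. A reader might infer that it is presented as a ranking of behaviors by impact. The text does not say so; the impact question comes from R3, under which item b is placed. Impact on elders is also to be judged through mood, engagement and competence (Analysis Plan), which this point does not touch.

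**The rejection rates describe a test the protocol never adopts.** This is also correct. They only give a scale.

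**The scope is narrow.** Walking and water are described under Year 2, and the service record may also hold other tasks. The point is limited to these two, although the protocol calls them the key activities.

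**Pay per walk.** A reader might add that walking-only participants are paid per walk (Subject compensation). The protocol states no link between payment group and health, so this does not support the point.

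**Conclusion.** The point holds for walking and water. As worded, and read in the natural way, item b cannot separate tailoring or refusal from effect, so it cannot by itself answer R3 for these tasks. The direction at the clinician-set level, favoring walking and against water, rests on the protocol's own examples. The direction for service received is uncertain, at least for water. The size is not derivable from the document; |r| of 0.12 to 0.28 with no true effect is what the assumed inputs give.

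A reader might infer that adjusting for baseline health cures the problem at the set level. It does so only if baseline health is measured without error and the reasons for tailoring carry no further information about later health. Dialysis or forgetfulness may well carry such information. The adjusted result must therefore also be called an association.

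The change is worth making, with medium confidence: it is cheap, and the extra fields may not be recoverable later.

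**What to change.** **Log**, for each elder and task: the clinician-set level (minutes, deliveries per day), the reason for any change from the base schedule, and the service offered, accepted and refused.

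**Reword item b** to:

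> For each task separately, later health status will be related to the clinician-set service level, adjusted for the same health measure taken before that deployment and for the recorded reason for tailoring. Service received will be reported descriptively. Both are associations and do not by themselves show which behavior has most impact.

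**Walking:** include only elders who were asked to walk; do not enter the others as zero.

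**Baseline value:** take it from the health tracking already planned, or from the record review or the optional SF-12 (Subject recruitment) if these are used for that purpose. Both are now described for recruitment and screening only.

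**Cost:** a few logged fields, a little more analysis and a more modest claim. Where a given reason nearly always leads to the same level, adjusting for it leaves little to compare, and the report should say so. Residual confounding remains. No tailoring, walking or water rule changes.

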### **Study duration**

1) We estimate that it will take three years from the date of IRB approval to enroll all subjects and complete the study. 2) A subject may choose to participate for as little as one focus group (1.5 - 2 hours) or may choose to participate in each part of the larger study over the course of three years. 3) 8/15/2014 - 8/15/2017

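### Item b correlates health with each elder's robot service record; if the record is a running total that includes elders who leave, health-related departure alone can link the two, and tailoring leaves the net sign open

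*Protocol*

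**What the plan says.** Under Procedures, item b in the Year 3 text reads: "Health status of subject participant will be tracked over years 2 and 3 and correlated with robot service record with the participant". It stands directly under the statement that R2 and R3 will be addressed. R3, in Overall objectives, asks how the robot can maintain and improve elders' health and which robot behaviours matter most for well-being. That is a causal question.

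Service is delivered in separate windows. The later Year 2 prototype "will be tested with elders and clinicians for 3 weeks", and the Year 3 prototype is tested at LIFE and/or a "LIFEaffiliated retirement community for 4 weeks". The first Year 2 test has no stated length. The training paragraph adds: "Those willing to participate in a week-long study will sign informed consents".

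Target population says of Kearsley and Mercy Douglas: "Members are 62 years and older, in imminent risk of a nursing home placement". LIFE members in general "are state-certified as nursing home eligible". Study duration lets a person attend a single focus group or stay for three years, and the compensation section treats continuing into Years 2 and 3 as optional.

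Service also depends on health by design. Clinicians or caregivers set the water frequency, with examples that raise it for certain conditions. Walks may be shortened for a painful condition, and only ambulatory elders are asked to walk.

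The Analysis Plan section does not mention item b and leaves final outcome metrics to be defined.

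**The concern.** A total service count is partly a measure of how long the elder was there to be served. In a frail population, length of stay plausibly depends on health. An elder who declines and leaves between the Year 2 and Year 3 windows would then contribute poor health and a short record, while an elder who stays well contributes the opposite. The two variables are tied through time present, even if the robot does nothing, nobody refuses service and nothing is tailored.

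The protocol offers item b as part of the answer to R3. A positive correlation could be read as the robot maintaining health when it may only show that healthier elders stayed longer. Nothing in item b separates the two explanations.

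**Working it through.** The protocol gives no sample size for item b, departure rate, effect size or significance level, so there is no figure of its own to reproduce. The check asks how large the correlation can be with no robot effect.

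**From the protocol.** The stated windows are 3 and 4 weeks, 7 in all. An elder who leaves between them loses 4/7 = 57% of the possible record.

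**Assumed.** 40 elders; a fraction p leaves after week 3; leavers are d SD worse in health; mean service is 7 per week (Poisson) with between-elder CV 0.4; two-sided 5% test.

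**Formulas.** Mean totals are 7 × 7 = 49 for stayers and 7 × 3 = 21 for leavers, a difference of 28.

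- Covariance of total T and health H: p(1−p) × d × 28
- Var(T) = p(1−p) × 28² + (1−p) × [49 + (0.4 × 49)²] + p × [21 + (0.4 × 21)²] = 784p(1−p) + 433.16(1−p) + 91.56p
- Var(H) = 1 + p(1−p)d²
- Chance of a positive test, by the Fisher transformation with m = atanh(r) × √37: Φ(m − 1.96) + Φ(−m − 1.96)

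| p | d | Covariance | SD(T) | SD(H) | r | Test positive |
|---|---|---|---|---|---|---|
| 10% | 0.5 | 1.26 | 21.67 | 1.011 | 0.06 | 6% |
| 10% | 1.0 | 2.52 | 21.67 | 1.044 | 0.11 | 10% |
| 30% | 0.5 | 2.94 | 22.26 | 1.026 | 0.13 | 12% |
| 30% | 1.0 | 5.88 | 22.26 | 1.100 | 0.24 | 32% |

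Simulation of the same settings (4,000 replicates each) gave mean r from 0.056 to 0.240 and positive tests in 6.1% to 32.4%. Repeat runs started at about 0.05, and one variant reached only 0.21 and 27% at the top.

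**A different model.** With 10-40% leaving, mean r was 0.08-0.18 when leaving was weakly tied to health (correlation 0.3) and 0.15-0.35 when strongly tied (0.6). With 30 elders the test was positive in 7-16% and 13-50% respectively. When leaving was unrelated to health, r was 0.00.

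**Dividing by time present.** With service per week present and no tailoring, mean r was about 0 and the test was positive in 4-6%.

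**Adding tailoring.** If sicker elders receive more service (assumed log-rate shift of −0.1 per SD of health), the cumulative correlation in the four settings above becomes −0.15, −0.10, −0.05 and +0.06. The sign reverses in three of the four. Under the same shift, service per week against health *level* gives −0.22 to −0.24, positive in 29-34%. Service rate against health *change* gives about 0, positive in 4-6%, for shifts of +0.1 and −0.1 alike.

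**The case against.** The strongest reply is that the protocol never says the record is a total. The Design section plans event-level data on requests, timing and success, so a rate could be computed, and such definitions are often left to an analysis plan, which is not shown. That limits the point: the bias is conditional. It does not remove it, because item b already names a plain correlation as a route to R3, and accumulated service is a natural reading that nothing excludes.

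Second, leavers must remain in the correlation. If health is not followed after departure they drop out, and in the settings above the null correlation is about 0. This is correct, but that analysis conditions on having stayed and discards elders whose departure may itself be a health outcome.

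Third, the size is fragile. If half the elders skip Year 3 for reasons unrelated to health (an assumption), r falls to 0.03-0.13 and the test is positive in 5-12%. The first Year 2 test is also left out of the 7 weeks for want of a stated length.

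Fourth, a per-time rate alone does not deal with tailoring and can look worse than the total when set against health level. This stands. It is why the rate has to be paired with health change or an adjustment for earlier health.

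**Conclusion.** The concern holds conditionally. If the record is accumulated service and leavers are kept, health-related departure produces a null correlation of about 0.05-0.24, with a nominal 5% test positive in about 6-32% of studies. These figures rest on 40 elders, 10-30% leaving, leavers 0.5-1 SD worse, and the assumed service rate and spread. None of these is in the protocol.

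A reader might infer three stronger things that the protocol does not support:

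- **That the bias makes the robot look beneficial.** This is true of the departure route alone. The protocol's own tailoring works in both directions and can cancel or reverse it.
- **That early departure in poor health is documented.** No departure rate is given. It is a plausible inference from the population.
- **That all elders are "in imminent risk of a nursing home placement".** That is said only of Kearsley and Mercy Douglas members. Elder-council and other LIFE members are described more broadly.

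This is a cheap improvement to a poorly chosen analysis, and it does not invalidate the study.

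**What to change.** Amend item b as follows:

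1. Express the service record as service per day that the elder was resident and eligible for the robot, within each test window. The 3-week, 4-week and week-long descriptions must be reconciled so that this denominator is defined.
2. Relate that rate to the change in health from before to after the window, or adjust for health before the window, using the health tracking already planned. Adjustment is the safer form where change itself depends on the starting level.
3. Include every elder with a later health value, without restricting to those present at the end. Report leavers with dates and reasons.
4. Report the result as a descriptive association, not as an effect of the robot on health.

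The cost is somewhat more than a change of wording: item b has no assessment schedule, so health values must be aligned to the test windows, and residence dates must be obtained from the sites. That is a small amount of extra data handling. No robot task or care arrangement needs to change.
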